Step ladder insertion technique: The AVF site will be cleaned with 2% chlorhexidine/alcohol 70% prior to needle insertion. If the patient develops contact dermatitis, the AVF site will be cleansed with 2% cholorhexidine, 70% alcohol, povidone iodine or antibacterial soap alone. Sites will be rotated with needles placed at least 2-3cms between needle tips.

Buttonhole insertion technique: The AVF site will be cleaned as above except cleansing will occur before and after buttonhole scab removal. A minimum of 2 buttonholes will be developed for patients undergoing double needle hemodialysis (1 for single needle) by a nurse or patient (at the discretion of the health care team) trained in the technique.

Buttonhole sites will be created at a 20-30 degree angle at least 3 cm from the arterial or venous anastomosis. Once the buttonhole is established with sharp needles, blunt needles will be used. At this time, the patient will be instructed on needle insertion technique if they were not taught to develop the buttonholes initially. Scabs will be removed from the buttonholes either with an alcohol or saline soaked gauze; the use of needles or tweezers to remove scabs will be discouraged.. Post hemodialysis, mupirocin (or other suitable antimicrobial cream if patient develops contact dermatitis/allergy, for example: polysporin, betadine ointment or PHMB antimicrobial dressings) will be applied to the buttonhole sites to reduce the risk of infection.

Time to Train

Patients will be trained according to usual home dialysis unit policies with the exception of the needle insertion protocol. Any difficulties with training needle insertion will be documented by the nurse educator. The time required to teach proficiency in self cannulation will be documented (the number of days required for the patient to competently place their own needles without the assistance of the dialysis nurse). Total training time will be the numbers of days required from start of training to discharge to home. Any missed days secondary to statutory holidays, appointments or other illness unrelated to access needle insertion technique will not be included in the training days calculation. If a patient has to return to the home dialysis unit to develop a new buttonhole site, the training time will also be documented and added to the total training time.

AVF Access Complications

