Any additional days of training and any days required for re-training will be included in the overall cost. Any differences in the cost of the blunt versus sharp needles and the mupirocin for buttonhole cannulation will be included in the overall cost. Treatment for infection including antibiotics and hospitalizations will be included and costed according to established principles. Similarly, the cost associated with any required angiogram (leading to an angioplasty), angioplasty or surgical revision will be included.

Visual Analogue Scale – Pain with Needling (Appendix 1)

All patients will continue (or start) with the step ladder insertion technique for the first 2 to 3 days at which time they will use the validated 10 cm visual analogue scale to rate the pain they experience with needle insertion. The visual analogue scale will be repeated at 2 additional time points – at the end of training and approximately 2 months after graduating home hemodialysis training. As many of the programs train 3 days per week, the additional time point is to capture the potential differences in perceived needling pain with increased frequency of needle insertion. It is unclear if buttonholes are easier to maintain when used more than 3 days per week as this may be associated with less pain on needle insertion. Topical anesthetics will not be withheld during assessments of pain with the visual analogue scale but the requirement for use will be documented.

Sample Size Calculation

There are a limited number of patients who start home HD each year in Canada. If we are unable to get at least 70% enrollment in the pilot study – it is very unlikely that we will be able to successfully undertake a study with a larger sample size. For the purposes of the feasibility pilot, the first 2 centres (Ottawa and University Health Network) will recruit participants for 18 months with the remaining centre's participating for 12 months. All patients who are eligible for the study will be approached for recruitment. Our goal is to demonstrate that we can successfully recruit. For the definitive study to explore the differences in training time between the two needle cannulation techniques: The mean number of training days for patients with an AVF in the FHN studies was 27.7 with a standard deviation of 10.4 (20). This was reduced by 5 days for patients using a central venous catheter. Assuming that a buttonhole cannulation would

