have a similar impact on training time, 69 patients per groups would give us 80% power to detect this difference. The number required in the trial increases to 107 if the difference is 4 days.

Analysis

For the purposes of the pilot study, basic demographic characteristics of the included and excluded patients will be described using appropriate descriptive statistics. This data will be retrospectively collected on patients who were not enrolled in the study. The percent of qualified patients enrolled in the study for the pilot study to be successful will be $\geq 70\%$. The secondary outcomes will be analyzed on an intent to treat basis upon completion of the main study assuming that this trial is feasible. The comparison of mean training times will be done with an un-paired t-test. A linear regression analysis will also be undertaken to examine predictors of training time including age, sex and Charlson comorbidity score in addition to needle insertion technique. Any differences in pain scores depending of frequency of cannulation will be explored within cannulation techniques. If no differences exist by frequency of cannulation, the data will be combined and the median pain scores will be assessed with a Wilcoxon rank sum test. The different types of complications and costs will be categorized and the overall mean differences will be assessed with an unpaired t-test. Any differences in outcomes by frequency of cannulation will also be explored within each of the secondary outcomes.

For patients who return to train on cannulation technique (started home HD with a CVC or other access that failed); their data will not be included in overall training time but all other study outcomes will be tracked and included in the analysis infections and complications.

The retrospectively collected demographic data will be analyzed in order to describe the patient population.

Data Safety Monitoring Board

Drs. [name] and [name] in addition to [name] (vascular access coordinator) have agreed to monitor the outcomes of this study. If we detect infection rates that are comparable to or greater to the benchmark for central venous catheters as adopted by the Ottawa Hospital - the study will be stopped (external benchmark bacteremia rate of 4.6 per 100 patient months, Nephrology News and Issues 2005, 37-43)

Study Investigators

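### Total training time adds return days after discharge for a new buttonhole site but for no other cannulation re-training, so the two arms' totals follow different rules

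*Combined protocol and SAP*

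**What the plan says.** The Time to Train section gives the base definition for both arms: "Total training time will be the numbers of days required from start of training to discharge to home". Days missed for holidays, appointments or illness unrelated to needling are left out. The section then makes one addition after discharge: "If a patient has to return to the home dialysis unit to develop a new buttonhole site, the training time will also be documented", and those days are to be "will also be documented and added to the total training time". No other return to the unit is mentioned, and no time limit is set on the addition.

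The Analysis section states: "The comparison of mean training times will be done with an un-paired t-test". It also says: "The secondary outcomes will be analyzed on an intent to treat basis upon completion of the main study assuming that this trial is feasible". Its own rule on returning patients is limited to one group: "For patients who return to train on cannulation technique (started home HD with a CVC or other access that failed"). Their data are kept out of overall training time.

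Two other outcomes treat re-training without regard to technique. The Secondary Objectives list re-trains for needling difficulty among the complications compared between arms, and Costs of Vascular Access includes all re-training days in overall cost.

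**The concern.** The sentence about new buttonhole sites refers to any patient, but the event belongs to one technique. Under intention to treat it falls on the buttonhole arm, crossovers aside. A step-ladder patient who goes home, cannot needle reliably and comes back for several days of re-training adds nothing to the total. A buttonhole patient who comes back for re-training at an existing site also adds nothing. A buttonhole patient who comes back for a new site adds every day.

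Counting the new-site days is fair, because they are real training effort. The problem is that comparable effort for other needling reasons is not counted, so part of any difference in means could come from the counting rule rather than the technique.

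This matters because the first secondary objective asks whether buttonhole cannulation shortens training, and the Sample Size Calculation sizes the definitive trial on that outcome. Under Study Investigators, the pilot data are to be retained for the definitive trial if feasibility is established, the sample size is achievable and no protocol changes are required. A definition set now could therefore carry through to the definitive comparison.

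**Working it through.** **1. The plan's own figure.** Inputs from the Sample Size Calculation: "The mean number of training days for patients with an AVF in the FHN studies was 27.7 with a standard deviation of 10.4", and "This was reduced by 5 days for patients using a central venous catheter". The plan states 69 per group for 80% power at 5 days, and 107 at 4 days. Significance level and allocation are not stated; I assume two-sided 0.05 and 1:1. The t-based solution is 68.9 per group for 5 days and 107.1 for 4 days, so both figures reproduce, with 107 as a per-group number. One-sided 0.05 would give 54.2 and 84.3, which do not match.

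**2. What each arm's total contains.** Define, as means per patient:
- F₁, F₂: days to first discharge, step-ladder and buttonhole;
- N: buttonhole return days for a new site;
- S: step-ladder re-training days after discharge;
- B: buttonhole re-training days after discharge that need no new site.

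| | Step-ladder | Buttonhole | Difference (step-ladder minus buttonhole) |
|---|---|---|---|
| All re-training counted | F₁ + S | F₂ + N + B | D = F₁ + S − F₂ − N − B |
| As written | F₁ | F₂ + N | F₁ − F₂ − N = D − (S − B) |

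The departure from a common rule is therefore S − B. If S exceeds B, the written rule understates the buttonhole advantage; if B exceeds S, it overstates it. The documents give neither quantity.

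**3. Hypothetical range.** Assume 0 to 20% of each arm return for 5 days of uncounted re-training. Then S and B each run from 0 to 0.20 × 5 = 1 day, and S − B runs from −1 to +1 day.

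**4. Scale.** With 69 per group and SD 10.4, the standard error of the difference is 10.4 × √(2/69) = 1.77 days. One day is 1/1.77 = 0.56 standard errors.

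**5. Consequences** (two-sided two-sample t-test at 0.05, SD held at 10.4):

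| S − B (days) | Expected difference when D = 5 | Power | When D = 0: chance of a significant result favouring step-ladder |
|---|---|---|---|
| −1 | 6 | 92% | 0.6% |
| −0.5 | 5.5 | 87% | 1.3% |
| 0 | 5 | 80% | 2.5% |
| +0.5 | 4.5 | 71% | 4.7% |
| +1 | 4 | 61% | 8.1% |

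When D = 0, the chance of a significant result favouring buttonhole is the mirror image: 8.1% at −1 day and 0.6% at +1 day.

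**6. What this does not show.** It is not a loss against the planned 5 days. That figure comes from training days with a catheter versus a fistula, and the plan does not say it includes re-training after discharge. D = 5 is used here only to set a scale.

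**7. Does another section repair it?** The Analysis rule on returning patients covers only those who started home dialysis with a catheter or with another access that failed. The cost and complication outcomes do take in re-training from both arms, but they do not feed the training-time total that the t-test compares. The separate record of days to competent self-cannulation does not say how later re-training is handled.

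**The case against.** The strongest reply is that the plan has one rule, not two. Returns that need no new site go uncounted in both arms, so re-training is treated alike. The only addition is for creating a new site, which repeats part of establishing the buttonhole technique and has no step-ladder counterpart. On this view the split is coherent: set-up goes into training time, and re-training goes into complications and cost, where both arms are covered. The authors may also simply have meant all re-training, in which case this is a gap in wording rather than a bias. Finally, the numbers are assumed: a full 1-day shift needs 20% returning in one arm and none in the other, equal return rates give no shift, and even the extreme is about half a standard error.

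Much of this stands. Uncounted re-training does occur in both arms, the size is hypothetical, and equal rates would cancel. Three things do not follow. The omission is not mere silence, because the definition ends the count at discharge and reopens it for one event only. The documents do not describe the split as deliberate. And the same label on uncounted days does not make the totals comparable: some buttonhole returns count and no step-ladder return can, while the documents give no reason to expect S and B to be equal.

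**Conclusion.** The concern holds. Followed as written, total training time admits return days for one event that only buttonhole cannulation can generate and leaves out all other cannulation re-training, so the t-test compares totals built by different rules. The one stated addition lengthens the buttonhole total, but the net departure from a common rule is S − B, and the documents fix neither its sign nor its size. The range of ±1 day, with power of 61% to 92% for a 5-day difference in full totals, rests on assumed return rates of 0 to 20% and an assumed 5 days per return.

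The effect is confined to the secondary comparison of training time. The feasibility outcome is untouched, and cost and complications already take re-training into account in both arms. The point should be settled because this comparison sizes the definitive trial and the pilot data may be kept for it. There is time to do so, since secondary outcomes are analysed only when the main study is complete.

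**What to change.** Rewrite the addition in Time to Train so that it does not depend on arm: return days for any cannulation-related re-training, including new buttonhole sites, are added to total training time in both arms. Count them over the same follow-up period in each arm. Twelve months is a natural choice, since it is the stated study length and the retention horizon in the first exclusion criterion. State how patients who leave before the end of that period are handled.

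Also report days from start of training to first discharge home in both arms. That summary is closest to the planning mean and SD, and it shows how much of any difference arises after discharge. Align the Analysis section with the new wording.

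The cost is a slightly longer definition and one extra summary. Re-training days in both arms are already needed for the cost analysis, so little or no new data collection should be required.

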Vanguard Multi-Centre Feasibility Trial to Determine if Buttonhole Versus Step-Ladder Cannulation for Home Hemodialysis is Associated with Reduced Overall Cost

Primary Objectives: To determine the feasibility of 1) randomizing patients to step-ladder versus buttonhole cannulation techniques, and 2) coordinating the multiple Canadian sites that are required for the definitive study.

Secondary Objectives: To determine 1) if buttonhole cannulation, compared to step-ladder cannulation is associated with reduced training time for home hemodialysis patients, 2) if buttonhole cannulation, compared to step-ladder cannulation is associated with reduced overall cost, 3) if buttonhole cannulation, compared to step-ladder cannulation is associated with reduced complications (infection – local and systemic, radiologic/surgical interventions, re-trains for needle insertion difficulties, hematoma formation, aneurysm formation, missed insertions), 4) if buttonhole cannulation, compared to step-ladder cannulation is associated with reduced patient discomfort with needling for intensive home hemodialysis patients, and 5) to describe the overall patient population to help explain recruitment challenges

Background

High Dose Hemodialysis

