All eligible patients will be randomized to either step ladder or buttonhole cannulation technique for needle insertion. Randomization will be determined via a computer generated randomization code with stratification by site and AVF type (incident vs. prevalent). The group assignment will be kept in sealed opaque envelopes and provided to sites via the coordinating centre at the time of study consent. Only the investigators will be aware of the training time as an objective of the study as the intervention cannot be blinded and the outcome is potentially influenced by factors other than needle insertion technique. For consent and the remainder of the health team; the purpose of the study will be to determine feasibility, infection rates and other complications associated with the two different needle insertion techniques. Each Research Ethics Board will need to approve that one of the study objectives will be concealed.

Data collection forms will be developed with the assistance of the Ottawa Hospital Methods Centre and pilot tested at 2 sites (Ottawa and University Health Network) prior to the creation of an electronic data capture form to be used by all participating sites. The amount of time required to consent patients, complete the case report forms and follow each patient for the complication outcomes will be documented at these two sites so that this data can be used to inform the definitive trial budget.

After ensuring that the case report forms and access documentation tool are useable and all necessary information is being collected, the remaining programs will begin to recruit patients. Each program will be responsible for keeping a log of all patients who are training for home hemodialysis and the proportion of patients who are candidates for the study. Of the patients that are candidates for the study, the number of patients who are randomized to the study will be tracked. Reasons for not participating in the study for all potential candidates will be documented and reviewed at quarterly meetings. If themes are identified that are limiting enrollment, solutions will be proposed by the investigators and implemented if possible.

Needle Insertion Techniques

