The definitive study will be part of the Canadian Intensive Hemodialysis Physician Group with representation from across Canada. The vanguard study will be collecting information from sites in Ottawa ([name]), Toronto (Drs. [name], [name] and [name]), Calgary ([name]) and Vancouver ([name]). All investigators have experience in high dose hemodialysis and clinical investigation. [name] has additional experience in economic analysis and [name] has just published a study of buttonhole versus stepladder cannulation in the in-centre conventional hemodialysis population. All

together, these sites train approximately 70 patients for high dose hemodialysis per year which will provide an adequate number of participants to ensure the success of this pilot study within the 2 years allotted for this grant. If no changes to the protocol are required, feasibility clearly established and sample size achievable, the pilot study data will be retained for the definitive trial.

Appendix 2

References:

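### The secondary outcomes are analysed only after a feasible main study is completed, so a vanguard whose data do not carry forward has no planned between-arm analysis

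*Combined protocol and SAP*

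**What the plan says.** The Secondary Objectives, on the opening page of the combined protocol and SAP, are those of the vanguard trial. Objectives 1 to 4 compare the arms on training time, cost, complications and needling pain. Two of them ask "if buttonhole cannulation, compared to step-ladder cannulation is associated with reduced overall cost" and "if buttonhole cannulation, compared to step-ladder cannulation is associated with reduced complications", and the complications listed include local and systemic infection. Objective 5 describes the patient population.

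The Study Overview gives the account of the study meant for consent and for the other staff: "the purpose of the study will be to determine feasibility, infection rates and other complications associated with the two different needle insertion techniques".

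The Analysis section gives the pilot two tasks. One is descriptive: "For the purposes of the pilot study, basic demographic characteristics of the included and excluded patients will be described using appropriate descriptive statistics". The other is the success criterion, which begins "The percent of qualified patients enrolled in the study for the pilot study to be successful will be" and sets the figure at 70% or more. On the secondary outcomes it says: "The secondary outcomes will be analyzed on an intent to treat basis upon completion of the main study assuming that this trial is feasible". The t-tests, the regression and the Wilcoxon test come after that sentence.

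The Sample Size Calculation says of enrolment below 70% that "it is very unlikely that we will be able to successfully undertake a study with a larger sample size". The Study Investigators section sets the terms for carrying data forward. Provided that the protocol needs no change, it requires "feasibility clearly established and sample size achievable, the pilot study data will be retained for the definitive trial".

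**The concern.** The rule for analysing objectives 1 to 4 depends on two events, feasibility and completion of a main study. The protocol foresees that the second may not happen. If it does not, the trial will have randomized patients, collected training, cost, complication and pain data on them, and have no stated occasion for comparing the arms.

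The Summary and Conclusions of the Background says that the two techniques have not been compared in a randomized trial of home patients, and it names infection as the risk that may offset the benefits. Even a small randomized comparison would therefore be worth reporting. Patients will also have been told that infection rates and other complications are what the study sets out to determine. Without a stated plan, the decision whether to analyse, and which outcomes to report, would be taken after the data could be seen.

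**Working it through.** **1. Following the rule through each outcome of the vanguard.**

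| Outcome of the vanguard | Does the Analysis trigger reach its data? | Analysis of objectives 1–4 |
|---|---|---|
| Feasible, data retained, definitive trial completed | Yes | Planned |
| Enrolment below 70%, no main study | No: neither condition is met | None stated |
| Feasible, but definitive trial not started or not completed | No: nothing is completed | None stated |
| Feasible, protocol changed, data not retained | No: the main study's analysis does not include them | None stated |

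The phrase about feasibility could refer to the vanguard or to the main study. The table is the same either way.

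**2. How likely is a miss of the 70% criterion?** The sites train about 70 patients a year (Study Investigators). The first two centres recruit for 18 months and the others for 12 (Sample Size Calculation). Trainees therefore number between 70 and 70 × 1.5 = 105, the latter an upper bound. The qualified share is not given, so I assume n = 20 to 105 qualified patients.

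With X ~ Binomial(n, p), the criterion is missed if X < c, where c is 0.7n rounded up.

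| n | c | p = 60% | 65% | 70% | 75% | 80% |
|---|---|---|---|---|---|---|
| 20 | 14 | 75% | 58% | 39% | 21% | 9% |
| 35 | 25 | 89% | 73% | 49% | 24% | 7% |
| 50 | 35 | 90% | 72% | 43% | 16% | 3% |
| 70 | 49 | 95% | 77% | 44% | 14% | 2% |
| 105 | 74 | 98% | 86% | 49% | 12% | 1% |

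Because c is a whole number, some intermediate n are less favourable. At n = 23, c = 17 (74%) and the chance of a miss is 56% at p = 70%. Over every integer from 20 to 105 the ranges are 75–99% at 60%, 39–56% at 70%, 10–35% at 75% and 1–16% at 80%.

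**3. What could a vanguard that misses 70% show?** I reproduce the plan's own sample size first. With SD 10.4 and a 5-day difference, and assuming two-sided alpha 0.05 and equal arms (neither is stated), n per arm = 2 × (1.96 + 0.842)² × 10.4² / 5² = 67.9. The t-test version gives 68.9, so the stated 69 reproduces. For 4 days the same formula gives 106.1, and the t-test version 107.1, against the stated 107.

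For such a vanguard I assume a qualified share of 30% to 100% and enrolment of 30% to 69%:

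- Smallest: 70 × 0.30 × 0.30 = 6.3 patients.
- Largest: 105 × 1.00 × 0.69 = 72.5 patients.
- The definitive comparison needs 2 × 69 = 138.

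Power for 5 days (two-sample t-test) runs from about 8% to 52%. The 95% half-width, t(0.975, 2m − 2) × 10.4 × √(2/m) with m per arm, runs from about 22 days (m = 3.15) to 4.9 days (m = 36.2). Patients returning to train are left out of the training-time analysis, so its usable numbers would be smaller still. Estimates with intervals are reasonable here; confirmatory tests are not.

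**The case against.** Deferral is sound practice when pilot data may join a definitive trial, because it avoids an early comparative look. That stands. The gap lies only where the data do not carry forward.

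Several stronger readings are tempting, and the documents do not support them:

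- *Every secondary objective would go unanswered.* No. Objective 5 is analysed in the pilot whatever the enrolment result, so at most four of the five are affected.
- *The methods would all be invented after the data were seen.* No. The Analysis section already names intention to treat, unpaired t-tests, a regression with listed covariates and a Wilcoxon test. What is missing is the occasion to apply them to vanguard data that do not carry forward.
- *Infection would go unexamined.* No. The Data Safety Monitoring Board section has a stopping rule against an external bacteremia benchmark of 4.6 per 100 patient months, which does not depend on feasibility. It makes no comparison between arms and does not cover training time, cost or pain.
- *The plan forbids analysis of a failed vanguard.* It does not say so. It states one trigger and is silent on what happens if that trigger is never met. The sponsor could still analyse the data, but not under a stated plan.
- *Failure is the expected result.* The documents do not support this. At a true enrolment of 80% a miss is unlikely. A miss also makes a larger study very unlikely in the protocol's own terms, not impossible.

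It is also fair to say that little information is at stake, since the sample would be small. This limits what can be concluded, but it does not justify having no planned report.

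**Conclusion.** The point holds for the branches in which the vanguard data are not carried into a completed definitive trial. There, the stated trigger leaves between-arm objectives 1 to 4 without a planned analysis, although they are objectives of this trial and the protocol itself foresees failure. This follows from the wording and rests on no calculation.

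How often it would matter depends on two quantities that the documents do not give, the number of qualified patients and the true enrolment rate. Under the assumed range, missing 70% is close to an even chance if true enrolment sits at the threshold, likely if it is 60%, and uncommon at 80%. These figures cover only the enrolment route; loss of the data through a protocol change would add to them. The change should be made. It is a correction to one rule and does not call the design into question.

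**What to change.** Replace the deferral sentence in the Analysis section with two branches, keyed to whether the pilot data are retained:

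- **(a) Pilot data retained for the definitive trial.** Hold the between-arm comparisons until that trial is completed.
- **(b) Progression criterion not met, definitive trial not started, or pilot data not retained for any reason, including a protocol change.** At the close of the vanguard, report secondary outcomes 1 to 4 by randomized arm on an intention-to-treat basis. Give estimates with 95% confidence intervals, with infections per unit of patient time. Label them exploratory and do no confirmatory testing.

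Keying the branches to retention matters. A rule that turned on the 70% criterion alone would miss a feasible pilot whose data are dropped after a protocol change.

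The cost is one paragraph of wording and a small amount of analysis, with no new data. Branch (a) leaves retained data uncompared, so the definitive trial's type I error is unaffected. The downside of branch (b) is that its estimates will be imprecise and must be presented as such.
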